8.2 Dose Modifications

CTEP-AERS reporting may be required for some adverse events (see Section [9.0](#)).

8.2.1 Tamoxifen therapy

There will be no dose reductions for Tamoxifen therapy. Tamoxifen therapy may be permanently discontinued at the discretion of the treating physician for other tamoxifen related toxicity.

Tamoxifen will be held for grade 3 or 4 hepatic function impairment. Resume tamoxifen therapy at the previous dose when hepatic toxicity resolves to \leq grade 1 or baseline.

If tamoxifen therapy is held for > 3 weeks (1 cycle), permanently discontinue protocol therapy.

Note: Vasomotor symptoms defined as flushing, hot flashes and sweating will be graded using the CTCAE Version 4.0. Please see Section [8.1.3](#) regarding instructions for treatment of these symptoms.

Note: Serious adverse events will be reported on CTEP-AERS using CTCAE v5.0.

8.2.2 Z-Endoxifen HCl

If a grade 3 or 4 lymphopenia, thrombocytopenia, or hypertriglyceridemia, hold Z-Endoxifen HCl therapy until toxicity resolves to < grade 2. Reduce dose to 40mg daily. If the toxicities do not resolve to ≤ grade 1 or baseline severity within 21 days (1 cycle), treatment is to be discontinued and the patient will go to event monitoring. If toxicity recurs, treatment is to be discontinued.

If a grade 3 or 4 non-hematologic event that is attributed to Z-Endoxifen HCl occurs, hold therapy until toxicity resolves to ≤ grade 1 or back to baseline (if baseline is grade 2) and reduce dose to 40mg daily. If the toxicities do not resolve to ≤ grade 1 or baseline severity within 21 days (1 cycle), treatment is to be discontinued and the patient will go to event monitoring.

The prompt reporting of adverse events is the responsibility of each investigator engaged in clinical research, as required by Federal Regulations. Adverse events must be described and graded using the terminology and grading categories defined in the NCI’s Common Terminology Criteria for Adverse Events (CTCAE), Version 4.0. The CTCAE is available at:

http://ctep.cancer.gov/protocolDevelopment/electronic_applications/ctc.htm. Attribution to protocol treatment for each adverse event must be determined by the investigator and reported on the required forms, using the codes provided.

Note: Serious adverse events will be reported on CTEP-AERS using CTCAE v5.0.

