7.1 Arm I Z-Endoxifen HCl

Agent	Dose	Route	Day	Retreatment Cycle
Z-Endoxifen HCl	80 mg	Oral (2 x 40mg capsule)	Days 1-21	Every 21 days (+/- 3 days)

1. Patients will take Z-Endoxifen HCl on an empty stomach (1 hour before or 2 hours after meals).
2. Patients should be instructed that the Z-Endoxifen HCl should be refrigerated. The Z-Endoxifen HCl should be dispensed with a cooler pack that the patient can use to transport this study medication.

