10.1.2 Formulation

Z-Endoxifen HCl as 40 mg (Swedish orange-colored size 2) capsules.

The capsules contain the inactive ingredients microcrystalline cellulose, ascorbic acid, sodium croscarmellose, colloidal silicon dioxide, and magnesium stearate. The capsules are packaged in high-density polyethylene (HDPE) bottles containing 30 capsules each.

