12.2 No disease Progression, Unacceptable Adverse Events

Those patients who have not had disease progression, but have experienced unacceptable toxicity may be eligible for retreatment at a lower dose (see [Section 8.0](#)).

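### Section 8.2.2 gives conflicting or unusable Z-Endoxifen instructions in three specific situations: return to a baseline of grade 2 or higher, attributed hypertriglyceridemia, and a further qualifying event in a patient already on 40 mg

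*Combined protocol and SAP*

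**What the plan says.** Section 8.2.2 has two dose-modification paragraphs.

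**First paragraph.** It opens "If a grade 3 or 4 lymphopenia, thrombocytopenia, or hypertriglyceridemia" and sets no attribution condition. The site is to "hold Z-Endoxifen HCl therapy until toxicity resolves to < grade 2. Reduce dose to 40mg daily". It continues: "If the toxicities do not resolve to ≤ grade 1 or baseline severity within 21 days (1 cycle), treatment is to be discontinued". Recurrence also ends treatment.

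**Second paragraph.** It covers grade 3–4 non-hematologic events attributed to Z-Endoxifen HCl. The site is to "hold therapy until toxicity resolves to ≤ grade 1 or back to baseline (if baseline is grade 2) and reduce dose to 40mg daily". The same 21-day discontinuation sentence follows. Nothing is said about recurrence.

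Other relevant text:

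- Section 7.1 sets the starting dose at 80 mg daily, "Oral (2 x 40mg capsule"), and Section 7.3 repeats it for crossover patients. Section 10.1.2 lists one strength: "Z-Endoxifen HCl as 40 mg (Swedish orange-colored size 2) capsules".
- Section 8.1.3 allows a dose reduction for persistent vasomotor symptoms and states no level.
- Section 12.2 says that patients without progression who "have experienced unacceptable toxicity may be eligible for retreatment at a lower dose", and refers back to Section 8.0. Sections 7.0 and 12.3 list unacceptable toxicity as a reason for ending treatment.
- Section 3.2.17 sets no entry limit for lymphocytes or triglycerides. The note to Section 3.3.7 caps toxicity from the listed prior therapies at grade 2.
- Sections 9.1 and 9.3 place hypertriglyceridemia under metabolism and nutrition disorders.

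**The concern.** A dose-modification rule has to give each patient one instruction that can be carried out. In three situations this one does not.

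**(a) Baseline grade 2 or higher.** In the first paragraph the restart sentence has no baseline exception, while the discontinuation sentence has one. A patient back at a grade 2 baseline meets neither.

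**(b) Attributed hypertriglyceridemia.** The first paragraph names it. It is also a non-hematologic event, so the second paragraph applies too, with a different baseline exception and no recurrence sentence.

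**(c) Already on 40 mg.** Both paragraphs order a reduction to 40 mg, whatever dose the patient is taking.

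At stake is whether sites handle the same safety event in the same way, in Arm I and after crossover.

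**Working it through.** The documents give no figure to reproduce. The check reads each sentence literally and follows it through.

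**Step 1: the two thresholds.** On whole-number grades, below grade 2 and at most grade 1 are the same condition. The different wording is therefore not itself a conflict; only the baseline clause can create one.

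**Step 2: rules as written.** Let B be the baseline grade and G the grade reached by day 21.

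- First paragraph, first event: restart if G < 2; discontinue if G > 1 and G > B.
- Second paragraph: restart if G ≤ 1, or if B = 2 and G ≤ 2; discontinue if G > 1 and G > B.
- First paragraph, recurrence: discontinue.
- If neither restart nor discontinuation is met, the hold has no stated end.

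**Step 3: first event**, with B and G each from 0 to 3 (4 × 4 = 16 combinations), for an event that meets both paragraphs:

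| Baseline B | Grade by day 21 | First paragraph | Second paragraph |
|---|---|---|---|
| 0 or 1 | 0–1 | restart at 40 mg | restart at 40 mg |
| 0 or 1 | 2–3 | discontinue | discontinue |
| 2 | 0–1 | restart at 40 mg | restart at 40 mg |
| 2 | 2 | **hold without end** | **restart at 40 mg** |
| 2 | 3 | discontinue | discontinue |
| 3 | 0–1 | restart at 40 mg | restart at 40 mg |
| 3 | 2–3 | **hold without end** | **hold without end** |

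All 8 combinations with baseline 0 or 1 agree. The first paragraph leaves an open hold in 3 of 16 combinations (B = 2 with G = 2; B = 3 with G = 2 or 3). The second does so in 2 of 16, both at B = 3. The paragraphs differ in one combination, B = 2 with G = 2.

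**Step 4: recurrent attributed hypertriglyceridemia.** The first paragraph discontinues in all 16 combinations. The second gives restart in 9 (2 + 2 + 3 + 2 for B = 0, 1, 2, 3), discontinuation in 5 (2 + 2 + 1 + 0) and an open hold in 2 (both at B = 3). The outcome differs in 9 + 2 = 11 of 16.

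**Step 5: patient already on 40 mg.** With whole 40 mg capsules taken daily, the only daily dose below 80 mg is 40 mg, and 8.2.2 names no other. An order to reduce to 40 mg is then empty in these cases:

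- a second attributed grade 3–4 non-hematologic event;
- a different first-paragraph toxicity after an earlier reduction;
- a first qualifying event after a vasomotor reduction under 8.1.3, if that reduction was to 40 mg.

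It does not arise when the same first-paragraph toxicity recurs, because that ends treatment.

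**Step 6: can the baselines occur?** Section 3.2.17 limits hemoglobin, platelets, creatinine, bilirubin and AST only. Grade 2 or higher lymphocyte or triglyceride values are not excluded there. The 3.3.7 note bars grade 3 when it comes from the listed prior therapies. Platelets have an entry floor, so no baseline route is claimed for thrombocytopenia.

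**Step 7: size.** Section 1.6 reports lymphocyte decrease in 22% and hypertriglyceridemia in 16% of 32 phase I patients, mostly grades 1–2, with grade 4 hypertriglyceridemia also reported. Grade 3–4 rates are not given. At an assumed 3–10%, 0.03 × 40 = 1.2 to 0.10 × 40 = 4 Arm I patients would use the rule at all. Only some of these would meet (a), (b) or (c), and that number could be zero.

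**The case against.** The strongest reply is that sites have sensible answers available. A rule that names hypertriglyceridemia would ordinarily prevail over a rule for a general class, which removes the overlap in (b). Section 12.2 is permissive, and 7.0 and 12.3 end treatment for unacceptable toxicity, which offers a fallback for (c). For baseline 0 or 1, presumably most patients, nothing conflicts.

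Part of this stands. Specific-over-general would settle (b), but the protocol does not state it. It would leave (a) in place, since the first paragraph's open hold at a grade 2 baseline remains. For (c), 12.2 points to a lower dose that Section 8 does not name, while 7.0 and 12.3 point to stopping, so the fallback is not clear.

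A reader might also infer more than the text supports:

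- **That one event can lead to restart, open hold or discontinuation.** No single combination yields all three. They need different baselines, or a first rather than a recurrent event.
- **That the missing attribution condition in the first paragraph is an error.** It is a rule that the sponsor may choose.
- **That the ambiguity halves exposure.** Table 1 in Section 1.6 does show a lower day-28 AUC at 40 mg than at 80 mg (6.42 against 15.4), but both paragraphs order 40 mg, so the fall follows from the common rule. A comparison with the 1 micromolar level in Section 1.4.4 would also ignore the 100–1000 nM range given in Section 1.1.
- **That PFS is biased.** Section 13.1 analyses patients in their randomized group regardless of actual treatment or its duration, and no PFS effect has been shown.

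**Conclusion.** The point holds in limited form. Read literally, 8.2.2 has an open-ended hold at baseline grade 2 or higher, two unranked rules for attributed grade 3–4 hypertriglyceridemia, and an order that cannot be carried out for a patient already on 40 mg unless the event is a recurrence of the same first-paragraph toxicity.

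This rests on three assumptions: grades are whole numbers, the recurrence sentence refers to the same toxicity, and capsules are taken whole every day. The number of patients affected is not given and is probably small. The case for changing the text is consistent safety handling in Arm I and the crossover phase. It is worth correcting, but it does not threaten the primary analysis.

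**What to change.** The sponsor should amend 8.2.2 so that:

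1. within each paragraph, the restart sentence and the day-21 discontinuation sentence treat baseline grade in the same way;
2. one stated paragraph governs hypertriglyceridemia;
3. the instruction for a patient already at 40 mg can be carried out and agrees with 7.0, 8.1.3, 12.2 and 12.3.

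The content of each rule is the sponsor's clinical decision, and none is proposed here. The cost is one text amendment to 8.2.2 with matching cross-references, and no new procedures or data collection.

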9.0 ADVERSE EVENTS

9.1 Routine Adverse Event Reporting

Adverse event data collection and reporting, which are required as part of every clinical trial are done to ensure the safety of patients enrolled in the studies as well as those who will enroll in future studies using similar agents. Adverse events are reported in a routine manner at scheduled times according to the study calendars in Section 5.0. For this trial, Adverse Events: Baseline, Adverse Events: Solicited and Adverse Events: Other forms are used for routine AE reporting in Rave.

Category (CTCAE SOC)	Adverse Event/ Symptoms	Baseline	Each evaluation	Grading scale (if not CTCAE)
Vascular disorders	Hot flashes	X	X	
	Thromboembolic events			
Metabolism and Nutrition disorders	Hypertriglyceridemia	X	X	
Investigations	Aspartate aminotransferase (AST) increased	X	X	

1. Patients who report visual symptoms in between their baseline and follow-up visits should be evaluated by ophthalmology.

9.2 Expedited Adverse event reporting (CTEP-AERS)

Investigators are required by Federal Regulations to report serious adverse events as defined in the table below. Alliance investigators are required to notify the Investigational Drug Branch (IDB), the Alliance Central Office, the Study Chair, and their Institutional Review Board if a patient has a reportable serious adverse event. The descriptions and grading scales found in the NCI Common Terminology Criteria for Adverse Events (CTCAE) Version 5.0 will be utilized for AE reporting as of April 1, 2018. The CTCAE is identified and located on the [CTEP website](http://ctep.cancer.gov/protocolDevelopment/electronic_applications/ctc.htm) at: http://ctep.cancer.gov/protocolDevelopment/electronic_applications/ctc.htm. All appropriate treatment areas should have access to a copy of the CTCAE. Expedited AE reporting for this study must only use CTEP-AERS (CTEP Adverse Event Reporting System), accessed via the CTEP home page, <http://ctep.cancer.gov>. In the rare occurrence when Internet connectivity is lost, a 24-hour notification is to be made to CTEP by telephone at [contact]. Once Internet connectivity is restored, the 24-hour notification phoned in must be entered electronically into CTEP-AERS by the original submitter at the site.

Note: All deaths on study require both routine and expedited reporting regardless of causality. Attribution to treatment or other cause should be provided.

9.2.1 Late Phase 2 and Phase 3 Studies: Expedited Reporting Requirements for Adverse Events that Occur on Studies under an IND/IDE ≤ 30 Days of the Last Administration of the Investigational Agent/Intervention ^{1,2}

FDA REPORTING REQUIREMENTS FOR SERIOUS ADVERSE EVENTS (21 CFR Part 312)

NOTE: Investigators **MUST** immediately report to the sponsor (NCI) **ANY** Serious Adverse Events, whether or not they are considered related to the investigational agent(s)/intervention (21 CFR 312.64)

An adverse event is considered serious if it results in **ANY** of the following outcomes:

- 1) Death
- 2) A life-threatening adverse event
- 3) An adverse event that results in inpatient hospitalization or prolongation of existing hospitalization for ≥ 24 hours
- 4) A persistent or significant incapacity or substantial disruption of the ability to conduct normal life functions
- 5) A congenital anomaly/birth defect.
- 6) Important Medical Events (IME) that may not result in death, be life threatening, or require hospitalization may be considered serious when, based upon medical judgment, they may jeopardize the patient or subject and may require medical or surgical intervention to prevent one of the outcomes listed in this definition. (FDA, 21 CFR 312.32; ICH E2A and ICH E6).

ALL SERIOUS adverse events that meet the above criteria **MUST** be immediately reported to the NCI via CTEP-AERS within the timeframes detailed in the table below.

Hospitalization	Grade 1 Timeframes	Grade 2 Timeframes	Grade 3 Timeframes	Grade 4 & 5 Timeframes
Resulting in Hospitalization ≥ 24 hrs	10 Calendar Days			24-Hour; 5 Calendar Days
Not resulting in Hospitalization ≥ 24 hrs	Not required		10 Calendar Days	

NOTE: Protocol specific exceptions to expedited reporting of serious adverse events are found in the Specific Protocol Exceptions to Expedited Reporting (SPEER) portion of the CAEPR

Expedited AE reporting timelines are defined as:

- “24-Hour; 5 Calendar Days” - The AE must initially be reported via CTEP-AERS ≤ 24 hours of learning of the AE, followed by a complete expedited report ≤ 5 calendar days of the initial 24-hour report.
- “10 Calendar Days” - A complete expedited report on the AE must be submitted ≤ 10 calendar days of learning of the AE.

¹ Serious adverse events that occur more than 30 days after the last administration of investigational agent/intervention and have an attribution of possible, probable, or definite require reporting as follows:

Expedited 24-hour notification followed by complete report ≤ 5 calendar days for:

- All Grade 4, and Grade 5 AEs

Expedited 10 calendar day reports for:

- Grade 2 adverse events resulting in hospitalization or prolongation of hospitalization
- Grade 3 adverse events

² For studies using PET or SPECT IND agents, the AE reporting period is limited to 10 radioactive half lives, rounded UP to the nearest whole day, after the agent/intervention was last administered. Footnote “1” above applies after this reporting period.

- Expedited AE reporting timelines defined:

➤ “24 hours; 5 calendar days” – The investigator must initially report the AE via AdEERS ≤ 24 hours of learning of the event followed by a complete CTEP-AERS report ≤ 5 calendar days of the initial 24-hour report.

➤ “10 calendar days” - A complete CTEP-

AERS report on the AE must be submitted ≤ 10 calendar days of the investigator learning of the event.

- Use the NCI protocol number and the protocol-specific patient ID provided during trial registration on all reports.

Additional Instructions or Exclusion to CTEP-AERS Expedited Reporting Requirements for Phase 2 and 3 Trials Utilizing an Agent Under a CTEP IND or non-CTEP IND:

- All adverse events reported via AdEERS (i.e., serious adverse events) should also be forwarded to your local IRB.

- Alliance A011203 uses a drug under a CTEP IND. The reporting requirements for investigational agents under a CTEP IND should be followed for all agents (any arm) in this trial.

- Reporting of cases of secondary AML/MDS is to be done using the NCI/CTEP Secondary AML/MDS Report Form. New primary malignancies should be reported using the study form Notice of New Primary.

Secondary Malignancy:

A *secondary malignancy* is a cancer caused by treatment for a previous malignancy (e.g., treatment with investigational agent/intervention, radiation or chemotherapy). A secondary malignancy is not considered a metastasis of the initial neoplasm.

CTEP requires all secondary malignancies that occur following treatment with an agent under an NCI IND/IDE be reported via AdEERS. Three options are available to describe the event:

- Leukemia secondary to oncology chemotherapy (e.g., acute myelocytic leukemia [AML])
- Myelodysplastic syndrome (MDS)
- Treatment-related secondary malignancy

Any malignancy possibly related to cancer treatment (including AML/MDS) should also be reported via the routine reporting mechanisms outlined in each protocol.

- Treatment expected adverse events include those listed in Section 10.0 and in the package insert.
- CTEP-AERS reports should be submitted electronically.
- When submitting CTEP-AERS reports for “Pregnancy”, “Pregnancy loss”, or “Neonatal loss”, the Pregnancy Information Form should be completed and submitted, along with any additional medical information (form is available on the CTEP web site at <http://ctep.cancer.gov/>). The potential risk of exposure of the fetus to the investigational agent(s) or chemotherapy agent(s) should be documented in the “Description of Event” section of the AdEERS report.

9.3 Z-Endoxifen HCl CAEPR

**Comprehensive Adverse Events and Potential Risks list (CAEPR)
for
Z-Endoxifen HCl (NSC 750393)**

The Comprehensive Adverse Events and Potential Risks list (CAEPR) provides a single list of reported and/or potential adverse events (AE) associated with an agent using a uniform presentation of events by body system. In addition to the comprehensive list, a subset, the Specific Protocol Exceptions to Expedited Reporting (SPEER), appears in a separate column and is identified with bold and italicized text. This subset of AEs (SPEER) is a list of events that are protocol specific exceptions to expedited reporting to NCI (except as noted below). Refer to the 'CTEP, NCI Guidelines: Adverse Event Reporting Requirements' http://ctep.cancer.gov/protocolDevelopment/electronic_applications/docs/aeguidelines.pdf for further clarification. *Frequency is provided based on 125 patients.* Below is the CAEPR for Z-Endoxifen HCl.

NOTE: Report AEs on the SPEER **ONLY IF** they exceed the grade noted in parentheses next to the AE in the SPEER. If this CAEPR is part of a combination protocol using multiple investigational agents and has an AE listed on different SPEERs, use the lower of the grades to determine if expedited reporting is required.

Version 2.0, September 25, 2017¹

Adverse Events with Possible Relationship to Z-Endoxifen HCl (CTCAE 5.0 Term) [n= 125]			Specific Protocol Exceptions to Expedited Reporting (SPEER)
Likely (>20%)	Less Likely (<=20%)	Rare but Serious (<3%)	
BLOOD AND LYMPHATIC SYSTEM DISORDERS			
Anemia			Anemia (Gr 2)
GASTROINTESTINAL DISORDERS			
	Constipation		
	Diarrhea		
	Dry mouth		
	Dyspepsia		
	Gastroesophageal reflux disease		
	Nausea		Nausea (Gr 2)
	Vomiting		
GENERAL DISORDERS AND ADMINISTRATION SITE CONDITIONS			
	Edema limbs		Edema limbs (Gr 2)
Fatigue			Fatigue (Gr 2)
INVESTIGATIONS			
	Alanine aminotransferase increased		Alanine aminotransferase increased (Gr 2)
	Aspartate aminotransferase increased		Aspartate aminotransferase increased (Gr 2)
	Cholesterol high		
Lymphocyte count decreased			Lymphocyte count decreased (Gr 2)
	Neutrophil count decreased		
	Platelet count decreased		Platelet count decreased (Gr 2)
	White blood cell decreased		White blood cell decreased (Gr 2)
METABOLISM AND NUTRITION DISORDERS			
	Anorexia		Anorexia (Gr 2)
	Hyperglycemia		

Adverse Events with Possible Relationship to Z-Endoxifen HCl (CTCAE 5.0 Term) [n= 125]			Specific Protocol Exceptions to Expedited Reporting (SPEER)
Likely (>20%)	Less Likely (<=20%)	Rare but Serious (<3%)	
	Hypertriglyceridemia		Hypertriglyceridemia (Gr 2)
	Hypoalbuminemia		
	Hypocalcemia		
	Hypophosphatemia		
		Tumor lysis syndrome	
MUSCULOSKELETAL AND CONNECTIVE TISSUE DISORDERS			
	Arthralgia		
	Myalgia		
NERVOUS SYSTEM DISORDERS			
	Dizziness		
	Dysgeusia		
	Headache		
	Hypersomnia		
	Peripheral sensory neuropathy		
PSYCHIATRIC DISORDERS			
	Agitation		
	Anxiety		
	Insomnia		Insomnia (Gr 2)
	Irritability		Irritability (Gr 2)
SKIN AND SUBCUTANEOUS TISSUE DISORDERS			
	Alopecia		
	Rash acneiform		
	Rash maculo-papular		
VASCULAR DISORDERS			
Hot flashes			Hot flashes (Gr 2)
	Hypertension		
	Thromboembolic event		

¹This table will be updated as the toxicity profile of the agent is revised. Updates will be distributed to all Principal Investigators at the time of revision. The current version can be obtained by contacting [contact]. Your name, the name of the investigator, the protocol and the agent should be included in the e-mail.

Adverse events reported on Z-Endoxifen HCl trials but for which there is insufficient evidence to suggest that there was a reasonable possibility that Z-Endoxifen HCl caused the adverse event:

- CARDIAC DISORDERS** - Sinus bradycardia
- EAR AND LABYRINTH DISORDERS** - Ear pain; Vestibular disorder
- ENDOCRINE DISORDERS** - Hyperthyroidism; Hypothyroidism
- EYE DISORDERS** - Blurred vision; Dry eye; Flashing lights; Floaters
- GASTROINTESTINAL DISORDERS** - Abdominal distension; Abdominal pain; Belching; Colonic perforation; Flatulence; Lip pain; Mucositis oral; Oral dysesthesia
- GENERAL DISORDERS AND ADMINISTRATION SITE CONDITIONS** - Chills; Edema face; Fever; Sudden death NOS
- INFECTIONS AND INFESTATIONS** - Infections and infestations - Other (infected hair follicle)
- INVESTIGATIONS** - Alkaline phosphatase increased; Blood bilirubin increased; Creatinine increased; INR increased; Investigations - Other (low HDL); Weight loss

METABOLISM AND NUTRITION DISORDERS - Dehydration; Hypercalcemia; Hyperkalemia; Hypermagnesemia; Hyponatremia; Hypokalemia; Hypomagnesemia; Hyponatremia

MUSCULOSKELETAL AND CONNECTIVE TISSUE DISORDERS - Bone pain; Buttock pain; Generalized muscle weakness

NERVOUS SYSTEM DISORDERS - Cognitive disturbance; Paresthesia; Seizure; Stroke

PSYCHIATRIC DISORDERS - Depression; Libido decreased

REPRODUCTIVE SYSTEM AND BREAST DISORDERS - Breast pain; Vaginal discharge; Vaginal dryness; Vaginal hemorrhage

RESPIRATORY, THORACIC AND MEDIASTINAL DISORDERS - Cough; Dyspnea; Sore throat

SKIN AND SUBCUTANEOUS TISSUE DISORDERS - Dry skin; Hyperhidrosis; Pruritus

VASCULAR DISORDERS - Peripheral ischemia

Note: Z-Endoxifen HCl in combination with other agents could cause an exacerbation of any adverse event currently known to be caused by the other agent, or the combination may result in events never previously associated with either agent.

